# Appendix G SELENA-SLEDAI Instrument

## SELENA-SLEDAI Flare Composite

### SELENA-SLEDAI (Systemic Lupus Erythematosus Disease Activity Index) INSTRUMENT SCORE

Check box: if descriptor is present at the time of visit or in the preceding 10 days.

Wt	Check if Present	Descriptor	Definition
8		Seizure	Recent onset (last 10 days). Exclude metabolic, infectious or drug cause, or seizure due to past irreversible CNS damage.
8		Psychosis	Altered ability to function in normal activity due to severe disturbance in the perception of reality. Include hallucinations; incoherence; marked loose associations; impoverished thought content; marked illogical thinking; bizarre, disorganized or catatonic behavior. Exclude uremia and drug causes.
8		Organic brain syndrome	Altered mental function with impaired orientation, memory or other intellectual function, with rapid onset and fluctuating clinical features. Include clouding of consciousness with reduced capacity to focus, and inability to sustain attention to environment, plus at least 2 of the following: perceptual disturbance, incoherent speech, insomnia or daytime drowsiness, or increased or decreased psychomotor activity. Exclude metabolic, infectious or drug causes.
8		Visual disturbance	Retinal and eye changes of SLE. Include cytoid bodies, retinal hemorrhages, serous exudate or hemorrhages in the choroid, optic neuritis, scleritis or episcleritis. Exclude hypertension, infection or drug causes.
8		Cranial nerve disorder	New onset of sensory or motor neuropathy involving cranial nerves. Include vertigo due to lupus.
8		Lupus headache	Severe persistent headache: may be migrainous, but must be nonresponsive to narcotic analgesia.
8		CVA	New onset of cerebrovascular accident(s). Exclude arteriosclerosis or hypertensive causes.
8		Vasculitis	Ulceration, gangrene, tender finger nodules, periungual infarction, splinter hemorrhages, or biopsy or angiogram proof of vasculitis.
4		Arthritis	More than 2 joints with pain and signs of inflammation (i.e., tenderness, swelling or effusion).
4		Myositis	Proximal muscle aching/weakness, associated with elevated creatine phosphokinase/aldolase or electromyogram changes or a biopsy showing myositis.
4		Urinary casts	Heme-granular or red blood cell casts.
4		Hematuria	>5 red blood cells/high power field. Exclude stone, infection or other cause.
4		Proteinuria	New onset or recent increase of more than 0.5 gm/24 hours.
4		Pyuria	>5 white blood cells/high power field. Exclude infection.
2		Rash	Ongoing inflammatory lupus rash.
2		Alopecia	Ongoing abnormal, patchy or diffuse loss of hair due to active lupus.
2		Mucosal ulcers	Ongoing oral or nasal ulcerations due to active lupus.
2		Pleurisy	Classic and severe pleuritic chest pain or pleural rub or effusion or new pleural thickening due to lupus.
2		Pericarditis	Classic and severe pericardial pain or rub or effusion, or electrocardiogram confirmation.
2		Low complement	Decrease in CH50, C3 or C4 below the lower limit of normal for testing laboratory.
2		Increased DNA binding	>25% binding by Farr assay or above normal range for testing laboratory.
1		Fever	>38°C. Exclude infectious cause.
1		Thrombocytopenia	<100,000 platelets/mm  .
1		Leukopenia	<3,000 white blood cells/mm  . Exclude drug causes.

_____ TOTAL SCORE (Sum of weights next to descriptors marked present)
			

Categorize as "Mild or Moderate" Flare or "Severe" Flare if the patient has at least one of the listed criteria in that category:	
Mild or Moderate Flare 	Severe Flare 
 Increase in SLEDAI $\geq$ 3 points, but not > 12	 Increase to a SLEDAI > 12
 New/worse: 
 
• Discoid, photosensitive, profundus, cutaneous vasculitis, bullous lupus
 
• Nasopharyngeal ulcers
 
• Pleuritis
 
• Pericarditis
 
• Arthritis
 
• Fever (SLE)
 
	 New/worse: 
 
• CNS-SLE
 
• Vasculitis
 
• Nephritis
 
• Myositis
 
• Platelet count < 60,000 (equivalent to <math>60 \times 10^9/L</math>)
 
• Hemolytic anemia: Hemoglobin <7.0 g/dL or decrease in Hemoglobin >3.0 g/dL
 
 Requiring a doubling of prednisone dose, or prednisone increase to >0.5 mg/kg/day, and/or hospitalization
 Increase in prednisone, but not to >0.5 mg/kg/day	 Increase in prednisone to >0.5 mg/kg/day
 Added NSAID or Plaquenil (hydroxychloroquine) for SLE activity	 New Cytoxan (cyclophosphamide), Azathioprine, Methotrexate for SLE activity
 Hospitalization for SLE activity	
 $\geq$ 1.0 Increase in Physician's Global Assessment (PGA) score, but not to more than 2.5	 Increase in Physician's Global Assessment (PGA) score to > 2.5

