#### **4.1.1 Rationale for HIV-1 immunization for persons with SLE**

It is unlikely that the vaccine regimen used in this study will provide direct protection against HIV-1 infection to participants. The primary immunological objective of this study is to determine whether an HIV-1 vaccine that can engage precursors of V1V2 glycan epitope bnAbs and has been associated with eliciting antibodies directed at the CD4 binding site can more robustly expand those pools of B cells in the presence of altered immune tolerance.

The specific rationale for performing the study in a group of persons with SLE is that 1) HIV-1 bnAbs have characteristics indicating they arose from B cells under immune tolerance control (i.e., lacking tolerance to self antigens) and persons with SLE are known to exhibit this type of altered immune tolerance, 2) several investigators have noted an underreporting of coincident SLE and HIV-1, and have suggested that SLE may permit protective immune responses and 3) a bnAb cross reactive with dsDNA was isolated from a person who had both SLE and HIV-1 (20, 28, 29). In addition, a recent study showed that autoimmune-prone mice immunized with HIV-1 Env were able to develop neutralization breadth (30).

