### 6.3.3.4 SELENA-SLEDAI

Box plots will be generated for baseline values and for values measured during the course of the study. Each box plot will show the first quartile, the median, and the third quartile. Outliers (values outside the box plot) will also be plotted. Each participant's points will be connected with a line. Summary statistics will be presented by study cohort and timepoint. A listing of participants who discontinue vaccination due to related SLE flares (of any severity), as defined in [Appendix G](#) and Section 7.3.3, will also be produced.

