### 9.8.1 Assessment of systemic and local symptoms

Systemic symptoms include increased body temperature, malaise and/or fatigue, myalgia, headache, chills, arthralgia, and nausea. Local symptoms include pain and/or tenderness at the injection site. The daily maximum severity reached for each symptom during the assessment period is reported.

Body temperature is measured by oral or infrared thermometry. All temperatures must be measured by non-axillary thermometry. This includes temperatures taken in the clinic, as well as temperatures taken by participants during the reactogenicity period.

Temperature is reported in degrees Celsius. If temperature is measured in Fahrenheit, the conversion to Celsius should be documented in the participant's chart note. A measurement is taken once daily during the assessment period and should be repeated if participant is feeling feverish.

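### SELENA-SLEDAI scores vaccine fever as lupus activity and scores serology on laboratory results alone, and Section 6.3.3.4 plans no breakdown by item

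*Combined protocol and SAP*

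**What the plan says.** Section 5.1 lists SELENA-SLEDAI among the primary safety endpoints. In Appendix G each descriptor is ticked "if descriptor is present at the time of visit or in the preceding 10 days". Three of its items matter here:

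- Fever, weight 1: ">38°C. Exclude infectious cause".
- Increased DNA binding, weight 2: ">25% binding by Farr assay or above normal range for testing laboratory".
- Low complement, weight 2: C3, C4 or CH50 below the laboratory's lower limit.

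Appendix G then places a participant in the mild or moderate flare category if any one listed criterion is met. One of these is "Increase in SLEDAI $\geq$ 3 points, but not > 12". Section 6.1.1.2 uses a different definition, a rise of 4 or more between visits.

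On the vaccine side, Table 4-1 lists fever among the less common reactions in the first days after injection. Section 9.8 sets a 7-day reactogenicity period, and Section 9.8.1 solicits temperature ("Systemic symptoms include increased body temperature").

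For analysis, Section 6.3.3.4 plans box plots with each participant's points joined, and a listing of participants who stop vaccination because of related flares. It adds: "Summary statistics will be presented by study cohort and timepoint". It plans no breakdown by item.

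**The concern.** The fever item rules out infection but not the vaccine. Other items in the same instrument do restrict cause: seizure and leukopenia exclude drug causes, and rash, alopecia and mucosal ulcers must be due to lupus. The flare list in Appendix G itself qualifies fever as SLE fever; the scored item does not. No passage in the protocol tells the scorer how to treat fever after vaccination.

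The two serologic items carry 4 points between them and need no symptom or sign. A rise made of fever and serology therefore enters the SELENA-SLEDAI summaries with the same value as new arthritis (4), or rash plus ulcers (2 + 2 = 4).

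At stake is how the SLE-activity part of primary objective 2 can be read. There is no concurrent control from which to subtract the artefact. RV328 participants did not have SLE, and the CHAVI 005 patients are an unvaccinated, cross-sectional group assigned to immunogenicity comparisons (Sections 4.3 and 6.3.2).

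**Working it through.** **The plan's own flare figure.** Section 6.1.1.2 projects 6.1 incidents a year at 3.9% per patient-month. As the expected number of participants with at least one flare, 16 × (1 − 0.961^12) = 16 × 0.3796 = 6.07, which agrees. The point below does not depend on this figure.

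**Score sums (weights from Appendix G).**

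- Fever 1 + DNA binding 2 = 3. This meets the Appendix G rise of 3 and falls short of the 4 in Section 6.1.1.2.
- DNA binding 2 + low complement 2 = 4. This meets both.
- Fever alone = 1, which meets neither. If vaccine fever were not scored, the first sum would drop to 2 and meet neither.

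**Can these items make a severe flare on score?** Exclusion criterion 6 removes scores above 4, so the entry score is 0 to 4. Fever plus DNA binding gives at most 4 + 3 = 7, the two serologic items at most 4 + 4 = 8, and all three at most 4 + 5 = 9. The severe category needs a score above 12, so the answer is no.

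**Who can gain the points?** Only a participant not already scoring the item at the comparison visit. Inclusion criterion 3 accepts positive anti-dsDNA as one route to entry. A participant already scoring DNA binding gains only 1 point from a fever. The documents do not give the share of such participants.

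**Timing.** Appendix F schedules SLE assessment at ten visits after the first dose: D7, D14, D28, D35, D42, D84, D168, D175, D182 and D238. Doses are on D0, D28 and D168. The look-back starts at visit day − 10:

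| Visit | Last dose | Look-back starts | Post-dose fever days captured |
|---|---|---|---|
| D7 | D0 | before the dose | 0-7 |
| D14 | D0 | D4 | 4-7 |
| D35 | D28 | before the dose | 0-7 |
| D42 | D28 | D32 | 4-7 |
| D175 | D168 | before the dose | 0-7 |
| D182 | D168 | D172 | 4-7 |

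Six of the ten visits overlap a reactogenicity window, three of them fully. Table 4-1 places fever in the first few days, so the 7-day visits matter most. Anti-dsDNA and complement are drawn at all six.

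**Frequency.** None is given. If a proportion q of participants had such a score-only rise, the chance of at least one among 16 is 1 − (1 − q)^16. For assumed q of 1%, 5%, 10% and 20% this is 14.9%, 56.0%, 81.5% and 97.2%. One participant is 1/16, about 6% of the cohort.

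**The case against.** The strongest reply is that little in the plan depends on these points, and much of it stands.

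- **Safety rules.** A reader might infer that score-only flares could pause the trial. Footnotes d and e of Table 11-8 require, beyond Appendix G, a rheumatologist's determination that the participant needs treatment before a mild or moderate flare counts. Discontinuation under Section 7.3.3 needs a related severe flare or a rheumatologist's judgement. The score sums alone do neither.
- **Analysis.** Section 6.3.3.4 plans no flare count, no test and no decision rule, so a few such points cannot decide the safety conclusion.
- **Double counting.** The same fever appears under reactogenicity and in the score, but these are separate outputs that are never pooled.
- **Other displays.** Anti-dsDNA and complement are local laboratory tests summarised by timepoint under Section 6.3.3.3, and RAPID3 is recorded. A careful reader could often recognise a serology-only rise. What is missing is the link from a given participant's rise to the items behind it.
- **The desired antibody read as disease.** This reading is tempting because Section 4.1.1 cites as rationale that "a bnAb cross reactive with dsDNA was isolated from a person who had both SLE and HIV-1". That antibody came from an HIV-infected person whose plasma also contained anti-dsDNA autoantibodies (Section 4.1). Section 4.3 says no prior AIDSVAX B/E vaccinee has developed bnAbs, and nothing shows that a vaccine-induced antibody would pass a serum cutoff. A rise in anti-dsDNA may also be a true safety signal, and the protocol monitors it as one. No vaccine mechanism for low complement is documented.

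The reply does not remove the fever problem. A non-infectious vaccine fever scores a point under the item as written.

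**Conclusion.** The point holds as a limit on interpretation. Vaccine fever adds 1 point of apparent lupus activity at up to six of the ten post-dose assessments. Fever with new DNA binding (3), or new DNA binding with low complement (4), reaches a flare threshold in the documents without clinical worsening. The consequence is confined to the descriptive SELENA-SLEDAI summaries and the Appendix G flare category.

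This rests on three assumptions: the item is scored as worded; the participant was not already scoring the serologic items concerned; and the Study Specific Procedures, which are not part of the documents, add no scoring guidance for vaccine fever. The frequency is unknown. The documents do not support saying that the vaccine response will turn the dsDNA item positive, that pause rules would be triggered, or that the trial's safety result hinges on this. The change is worth making because it is cheap and is best fixed before results are seen.

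**What to change.** In Section 6.3.3.4:

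1. Keep the total score and its planned displays.
2. Add, as a supplementary display, a clinical score that omits the DNA-binding and low-complement items, and omits fever with onset in the 7-day reactogenicity period unless the rheumatologist attributes it to SLE.
3. List every SELENA-SLEDAI rise of 3 or more with the items that produced it. This also covers the 4-point definition in Section 6.1.1.2. That definition and the 3-point criterion in Appendix G should be reconciled, or each tied to its own use.

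Leave the pause, review and care rules unchanged.

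The item ticks are on the Appendix G form, and fever onset is in the reactogenicity records. The rheumatologist's attribution of a fever should be noted at the visit if the form does not already capture it. The cost is SAP wording, one derived score and one listing. The downside is a second version of the score to present. Because it leaves out serologic activity, it should supplement the total and not replace it.

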As part of the original Center for HIV-AIDS Vaccine Immunology (CHAVI) program, the CHAVI 005 study examined a group of participants with known autoimmune disease to determine if any had undiagnosed HIV-1 infection, and if their plasma had any evidence of existing neutralizing antibodies that could account for the previously noted disparity between SLE and HIV-1 infection. This cohort, including 100 participants without autoimmune disease and 125 participants with SLE, was recruited from the Duke Lupus Clinic between 2005-2011. The CHAVI program tested this cohort using both HIV-1 antibody and viral load assays and found that none of the participants were HIV-1-infected. Testing of a subset of the participants did not reveal evidence of HIV-1 neutralizing antibodies or reactivity with HIV-1 Env proteins, although it should be noted that the study participants did not receive any HIV-1 vaccinations. Samples from this study are available for testing using the same assays planned for the present study, and for all participants, there are plasma, serum, and PBMC stored in the CHAVI Repository. This cohort was drawn from the same patient population at Duke that will be recruited for this study, and because the second of two sites participating in this study is in Alabama, the demographics of the two populations is likely to be similar. We can therefore use the SLE patients in the CHAVI 005 study as unvaccinated SLE controls, serving as a cross-sectional comparison group.

The primary outcome is to evaluate whether persons with SLE vaccinated with an HIV-1 vaccine will develop HIV-1 nAbs with greater breadth and potency than persons without SLE. In addition, our immunogenicity hypotheses are that this cohort of participants with SLE will make a qualitatively and quantitatively superior antibody response against HIV-1. An additional secondary outcome will address the hypothesis that the vaccine regimen will be safe and well tolerated by participants. The proposed number of participants is not sufficiently powered to detect uncommon or rare events. Participants will be monitored for sentinel events indicative of SLE disease activation (ie, SLE flare); detection of an SLE flare will trigger additional review.

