### 7.3.3 Discontinuing vaccination for a participant

Under certain circumstances, an individual participant's vaccinations will be permanently discontinued. Specific events that will result in stopping a participant's vaccination schedule include:

- Co-enrollment in a study with an investigational research agent (rare exceptions allowing for the continuation of vaccinations may be granted with the unanimous consent of the HVTN 121 PSRT)
- Clinically significant condition (ie, a condition that affects the immune system or for which continued vaccinations and/or blood draws may pose additional risk), including but not limited to the following:
  - Pregnancy (regardless of outcome)
  - HIV infection
  - Any grade 4 local or systemic reactogenicity symptom, lab abnormality, or AE that is subsequently considered to be related to vaccination
  - Any grade 3 lab abnormality that is subsequently considered to be related to vaccination
  - Other grade 3 clinical AE that is subsequently considered to be related to vaccination with the exception of fever, vomiting, and subjective local and systemic symptoms. For grade 3 injection site erythema and/or induration, upon review, the HVTN 121 PSRT may allow continuation of vaccination
  - SAE that is subsequently considered to be related to vaccination
  - Clinically significant type 1 hypersensitivity reaction associated with study vaccination. Consultation with the HVTN 121 PSRT is required prior to subsequent vaccinations following any type 1 hypersensitivity reaction associated with study vaccination
  - Related "Severe" SLE flare, as defined by application of the SELENA-SLEDAI instrument ([Appendix G](#))
  - SLE flare is defined clinically by a rheumatologist as severe enough to warrant discontinuation of vaccination
  - New use of mycophenolate mofetil

- Investigator determination in consultation with Protocol Team leadership (e.g., for repeated nonadherence to study staff instructions)

Participants discontinuing study product for reasons other than HIV infection should be counseled on the importance of continuing with the study and strongly encouraged to participate in follow-up visits and protocol-related procedures per the protocol for the remainder of the trial, unless medically contraindicated (see HVTN 121 SSP).

Participants diagnosed with HIV infection during the study should be encouraged to participate in follow-up visits as indicated in Section [9.12](#).

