**Table 11-8 AE notification and safety pause/AE review rules**

Event and relationship to study products	Severity	HVTN CRS action a	HVTN Core action
SAE, related	Grade 5 or Grade 4	Phone immediately, email and submit forms immediately	Immediate pause
SAE, not related	Grade 5	Phone immediately, email and submit forms immediately	Immediate PSRT notification
SAE, related	Grade 3, 2, or 1	Email and submit forms immediately	Immediate PSRT notification and prompt PSRT AE review to consider pause
AE b , related	Grade 4 or 3	Email and submit forms immediately	Immediate PSRT notification and prompt PSRT AE review to consider pause
“Severe” c SLE flare, regardless of relationship	N/A	Phone immediately, email and submit forms immediately	Prompt PSRT AE review
“Mild or moderate” d,e SLE flare, related	N/A	Phone immediately, email and submit forms immediately	Prompt PSRT AE review
3 or more confirmed “moderate” or “severe” SLE flares, regardless of relatedness	N/A	Phone immediately, email and submit forms immediately	Immediate pause

a Email addresses are found on the Protocol home page on the HVTN Members’ site (<https://members.hvtn.org/protocols/hvtn121>). Phone numbers for each pause rule are in the HVTN 121 SSPs.

b Does not include the following Grade 3 subjective reactogenicity symptoms: injection site pain, tenderness, fatigue/malaise, myalgia, arthralgia, chills, headache, nausea (unless IV rehydration required).

c “Severe” SLE flare is defined by application of the SELENA-SLEDAI instrument ([Appendix G](#)).

d “Moderate” SLE flare is defined by application of the SELENA-SLEDAI instrument ([Appendix G](#)), as well as the determination by a rheumatologist that the participant has flare components/symptoms/lab indices necessitating treatment with a dosage of Prednisone (or equivalent) in the range of >7.5 mg/day to < 0.5 mg/kg/day.

e “Mild” SLE flare is defined by application of the SELENA-SLEDAI instrument ([Appendix G](#)), as well as the determination by a rheumatologist that the participant has flare components/symptoms/lab indices necessitating treatment with a dosage of Prednisone (or equivalent) of ≤7.5 mg/day.

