For all safety pauses, HVTN Core notifies the HVTN 121 PSRT, HVTN Regulatory Affairs, DAIDS Pharmaceutical Affairs Branch (PAB), DAIDS Regulatory Affairs Branch (RAB), DAIDS Safety and Pharmacovigilance Team (SPT), and participating HVTN CRSs. When an immediate safety pause is triggered, HVTN Core notifies the SMB.

Once a trial is paused, the HVTN 121 PSRT reviews safety data and decides whether the pause can be lifted or permanent discontinuation of vaccination is appropriate, consulting the SMB if necessary. HVTN Core notifies the participating HVTN CRSs, HVTN Regulatory Affairs, DAIDS PAB, DAIDS RAB, and DAIDS SPT of the decision regarding resumption or discontinuation of study vaccinations. Based on the HVTN 121 PSRT assessment, DAIDS RAB notifies the FDA as needed.

If an immediate HVTN 121 PSRT notification or prompt HVTN 121 PSRT AE review is triggered, HVTN Core notifies the HVTN 121 PSRT as soon as possible

during working hours (local time)—or, if the information was received during off hours, by the morning of the next work day. If a prompt HVTN 121 PSRT AE review cannot be completed within 72 hours of notification (excluding weekends and US federal holidays), an automatic safety pause occurs.

The HVTN requires that each CRS submit to its IRB/EC and any applicable RE protocol-related safety information (such as IND safety reports, notification of vaccine holds due to the pause rules, unanticipated problems involving risks to participants or others, and notification of other unplanned safety pauses). CRSs must also follow all applicable RE reporting requirements.

In addition, all other AEs are reviewed routinely by the HVTN 121 PSRT (see Section [11.4.2](#)).

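### A flare treated with newly started mycophenolate, leflunomide, rituximab or belimumab can fall outside Table 11-8's severe-flare review and three-flare pause, while the same flare treated with azathioprine falls inside both

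*Combined protocol and SAP*

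**What the plan says.** Appendix G sorts flares into two columns, mild or moderate and severe; one listed criterion is enough. The severe drug criterion reads "New Cytoxan (cyclophosphamide), Azathioprine, Methotrexate for SLE activity". The mild-or-moderate drug criterion covers an added NSAID or hydroxychloroquine. The other severe routes are a SLEDAI rise to above 12, prednisone raised above 0.5 mg/kg/day, a Physician's Global Assessment above 2.5, and listed organ or blood involvement. As printed, the last of these counts only if it requires doubled prednisone, prednisone above 0.5 mg/kg/day, and/or hospitalization.

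Table 11-8 in section 11.3 applies these categories in three rows:

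- Severe "SLE flare, regardless of relationship": prompt PSRT review.
- Mild or moderate flare: prompt PSRT review, but only if related.
- Three or more confirmed moderate or severe "SLE flares, regardless of relatedness": immediate pause.

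Footnote c defines severe by Appendix G alone. Footnote d makes a flare moderate only if a rheumatologist also finds features "necessitating treatment with a dosage of Prednisone (or equivalent) in the range of >7.5 mg/day to < 0.5 mg/kg/day". Footnote e sets mild at a need of 7.5 mg/day or less.

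Section 11.3 puts a deadline on prompt review: if it "cannot be completed within 72 hours of notification (excluding weekends and US federal holidays), an automatic safety pause occurs".

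For the individual participant, section 7.3.3 ends vaccination on "New use of mycophenolate mofetil", with no relatedness condition, and separately for a related severe "SLE flare, as defined by application of the SELENA-SLEDAI instrument". Section 7.2 names rituximab and belimumab (criterion 13) and mycophenolate, leflunomide, methotrexate, azathioprine and cyclophosphamide (criterion 14) as excluding treatments.

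**The concern.** The flare rows of Table 11-8 are the only automatic trial-level response to a lupus flare as such, and flare is the main risk specific to this population. The severe row and the pause row deliberately set attribution aside. That is sensible in a single-arm, open-label study, where it is hard to tell a vaccine effect from background disease in one participant.

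Because severe is tied to a list of three drugs, whether those rows operate can depend on which immunosuppressant the treating physician chose. A flare that led to mycophenolate, leflunomide or a B-cell agent may have been as serious as one that led to azathioprine. Yet following the plan exactly can withhold the timed review and the place in the pause count.

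**Working it through.** No sample-size or power figure bears on this point. The check is to run one flare through the rules as written.

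**The flare.** SLEDAI rises by at least 3 points but not above 12, so the mild-or-moderate category is met. There is no prednisone increase above 0.5 mg/kg/day, no Physician's Global Assessment above 2.5, no hospitalization, and no organ involvement that meets its steroid or hospitalization condition. One of the four unlisted drugs is newly started for lupus activity.

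**Step 1, category.** None of the four drugs appears in either column of Appendix G, so the drug start does not change the category. The flare is mild or moderate. With azathioprine instead, the severe drug row applies at once.

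**Step 2, other rows.** No row of Table 11-8 is triggered by a drug start or by a stop under section 7.3.3. The general adverse-event row and most serious-event rows require relatedness. The one row for unrelated serious events is for deaths.

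**Step 3, cross prednisone need with attribution.**

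| Prednisone need | Attribution | Unlisted drug: mandated prompt review | Unlisted drug: counts toward pause | Azathioprine: review / count |
|---|---|---|---|---|
| None | Unrelated | No | No | Yes / Yes |
| Up to 7.5 mg/day | Unrelated | No | No | Yes / Yes |
| >7.5 mg/day to <0.5 mg/kg/day | Unrelated | No | Yes | Yes / Yes |
| None | Related | Yes | No | Yes / Yes |
| Up to 7.5 mg/day | Related | Yes | No | Yes / Yes |
| >7.5 mg/day to <0.5 mg/kg/day | Related | Yes | Yes | Yes / Yes |

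With an unlisted drug, 3 of 6 combinations carry no mandated review, 4 of 6 are not counted, and 2 of 6 miss both. With azathioprine, none misses either. These are counts of rule outcomes and say nothing about how often each arises.

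**Step 4, consequence per flare.** An unrelated flare on this path loses one timed review. An uncounted flare means that the immediate pause needs one more counted flare, for example a fourth flare where the third would have sufficed.

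**Step 5, what still operates.** Safety forms, including those for adverse events and concomitant medications, are due by the end of the next business day (11.2.1). HVTN Core monitors safety daily (2.5), although 11.1.4 and 11.4.1 direct that work mainly at events that meet the reporting, pause or review criteria. The PSRT, which includes a rheumatologist (11.1.1), reviews reports weekly in the injection phase (11.4.2) and may suspend vaccination outside the table (11.3). Section 4.3 adds that "detection of an SLE flare will trigger additional review", but names no reviewer or deadline.

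**The case against.** The best case against raising this has four parts.

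- **The path is narrow.** Many flares serious enough for these drugs will meet another severe criterion, and a related flare still gets prompt review. The pause count turns on the prednisone need that the rheumatologist finds, so drug choice is not the only determinant. This stands, and it is why the point is small. It does not close the path: the organ criteria carry a steroid or hospitalization condition, so an outpatient flare managed with little steroid can miss them.
- **Awareness is not lost.** Correct. What is lost is the 72-hour deadline with its automatic pause, and a place in the count.
- **A standard instrument should not be altered.** Agreed, and it need not be. Footnotes d and e already add study-specific conditions to Appendix G for use in Table 11-8.
- **A participant-level stop needs no trial-level counterpart.** Also fair; pregnancy has none. The point does not depend on section 7.3.3.

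That last part bears on a stronger reading. A reader might infer that the protocol has its order reversed: mycophenolate, a named permanent stop, sets off nothing at trial level, while azathioprine, which is not a named stop, sets off everything. The documents do not support this. Section 7.3.3 lists conditions that affect the immune system or add risk, alongside pregnancy and HIV infection. It does not rank flare severity, and it is expressly open-ended, so a new azathioprine start could lead to a stop under the same heading. Nor is mycophenolate the only omission: a remedy for that drug alone would leave the same dependence on drug choice for leflunomide, rituximab and belimumab.

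**Conclusion.** The gap is real and follows from the text. A flare treated with one of the four unlisted agents and meeting no other severe criterion can miss the mandated prompt review, the three-flare count, or both. The size is one review and one count per such flare. It is a minor point, worth correcting because it sits in a safety rule and costs almost nothing.

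Frequency is not in the documents and is probably very small, so no numerical loss is claimed. A reader might try to supply one from section 6.1.1.2. At 3.9% per patient-month, 16 × (1 − 0.961^12) = 6.07, which agrees with the plan's 6.1 for a year. The same formula at six months gives 16 × (1 − 0.961^6) = 3.40, which looks close to three. That comparison does not hold. The 3.40 counts participants with a flare of any severity, whereas the rule counts confirmed moderate or severe flares. The rate is also a background figure from the control arm of a cited study of flare in pregnancy. It says nothing about the share treated with these drugs or about lost detection of vaccine harm.

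The conclusion assumes that Table 11-8 and Appendix G are applied as printed. The Study Specific Procedures are not among the documents and might add handling for such flares.

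**What to change.** Leave Appendix G as printed. Add one footnote to Table 11-8: for the severe-flare prompt-review row and the three-flare pause row, a flare treated with newly started mycophenolate, leflunomide, rituximab or belimumab for SLE activity is handled as severe. Section 7.3.3 and flare reporting keep the unmodified instrument.

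No new data are needed, since concomitant medications are already collected at clinic visits. The cost is an occasional extra prompt review or a slightly earlier pause. Severe will also mean something slightly wider in two rows than elsewhere, so sites must be told that the footnote applies to those two rows only.
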